Design: A Phase III, randomised, triple-blind, placebo-controlled, parallel-group multicentre trial of vitamin D3 supplementation. Overall, 323 (of the target of 865) children aged 1-5 years, with asthma triggered by URTI, ≥ 4 URTIs in past year (or ≥ 2 URTIs in past 12 months if pertaining to the pandemic period) and ≥ 1 OCS in the past 6 months (12 months since February 2022) were recruited in 9 or more Canadian centers over a 7-year period in this high-intensity 7-month protocol. Year-round, children were randomly assigned to one of the two following study arms: (1) Intervention—two oral boluses of 100,000 IU vitamin D3 (3.5 months apart) with 400 IU daily vitamin D3 or (2) Control—identical placebo boluses with daily placebo dose.

Research question: Can vitamin D3 supplementation decrease the number of asthma exacerbations per child requiring rescue OCS (predominantly physician-initiated) vs placebo?

Randomisation was implemented through the Applied Clinical Research Unit (ACRU), at the CHUSJ, under the direction of the study statistician, [name]. A computer-generated random list was utilized, with randomisation stratified by site to ensure balanced allocation across different locations. Children were allocated to either the vitamin D3 or placebo group in a 1:1 ratio using a permuted block randomisation method, which enhanced allocation concealment. Group allocation codes for each site were securely stored with restricted access by the Central Pharmacy (CHUSJ) and the independent biostatistician. The active vitamin D3 and placebo preparations, provided by the manufacturer Europharm, were identical in appearance and taste, ensuring blinding. The allocated treatment numbers were forwarded to site pharmacies, which prepared the bolus in coded syringes and the coded bottles containing the daily dose and dispensed the study drugs in masked kits to maintain the integrity of the randomisation process.

Analysis objectives

The primary objective of this analysis is to evaluate whether vitamin D3 supplementation leads to a 25% relative reduction in the mean number of exacerbations requiring oral corticosteroids (OCS) per child over a 7-month period compared to placebo. We hypothesized that the number of OCS per child would approximately follow a Poisson distribution.

The secondary objectives are to assess differences between the treatment groups in:

- Mean number and type of laboratory-confirmed respiratory infections during asthma exacerbations.

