Source documents anonymized and retained in the patient study binder include pharmacy records, medical records, relevant information from Dossier de Santé du Québec (DSQ) or similar databases if obtained by the treating physician, laboratory results, and pulmonary function test results.

The data is organized in a tabular format within REDCap, with each row representing a participant observation (one row per event per person) and each column representing a specific data field. Data exports are available in CSV, Excel, and XML formats. The data fields include various types such as text, number, date, and multiple choice. The data dictionary is accessible within the REDCap project and provides detailed descriptions of each data field, including field names, types and allowed values.

Samples and Laboratory Databases:

- Biobank log (xlsx file, managed by the study Coordination Centre)
- CHUSJ Lab results for urine and blood (xlsx file, uploaded directly to OwnCloud),
- McMaster University Lab results for nasal swabs (xlsx file, uploaded directly to OwnCloud),
- Oscillometry results (data exported from the Tremoflo software, managed by the study Coordination Centre)

The detailed description of samples/data transfer and storage is described in the Data Management Plan.

Analysis sets/Populations/Subgroups

The target population for this study includes children aged 1-5 years with physician-diagnosed asthma, who have experienced recurrent, moderate/severe viral-induced exacerbations in the

preceding year. These children were treated with daily or pre-emptive inhaled corticosteroids (ICS) alone or with adjunct therapy as the standard of care from randomization onwards, and were randomized to receive either vitamin D3 supplementation or placebo. The sampling frame consists of potentially eligible children seen in one of the 9 participating pediatric institutions. Recruitment occurred in the fall over 3 months (Sept to Nov) for 1 year (2018), over 5 months per year (from Sept to January) for 3 years (2019-2021), than year-round for another 3 years (2022-2024), over a total period of 7 years. The analysis sample (n=323) includes all randomized participants regardless of adherence to the intervention protocol or whether they completed the study (intention-to-treat analysis). Of note, the consent form allowed data collection of the primary outcome until 7 months post-randomization, even in case of withdrawals or loss to follow-up.

Inclusion criteria:

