- Age 1-5 years
- Physician-diagnosed asthma (as per the 2015 Canadian Position Paper on the diagnosis of preschool asthma)
- ≥ 1 asthma exacerbation requiring rescue oral corticosteroids (OCS) in the past 6 months or ≥ 2 in the past 12 months from 2018 until 2020; then ≥ 1 asthma exacerbation requiring rescue oral corticosteroids (OCS) in the past 12 months, starting from the fall of 2020 (pandemic) onwards (as documented by pharmacy/medical records)
- ≥ 4 upper respiratory tract infections (URTIs) in the past 12 months (as per parental report) or ≥ 2 URTIs in past 12 months, starting from the fall of 2020 (pandemic) onwards
- URTIs as the main asthma trigger (as per parental report).

The inclusion criteria target a high-mordidity population, at risk of consequences from asthma exacerbations, ensuring they are the most likely to benefit from the treatment.

Exclusion criteria:

- Intake > 400 IU/day of vitamin D3 supplements or fish oil in the past 3 months
- Intention to use > 400 IU/day of vitamin D3 supplements or fish oil in the fall and winter
- Extreme prematurity (< 28 -week gestation)
- No vitamin D supplementation (if breast-fed in the last 6 months)
- Vitamin D restrictive diets, that is, minimal intake of vitamin D fortified milk (< 250 mL/day for 1-3 years or < 375 mL/day for 4-6 years) AND no other (or < 200 IU/day) vitamin D supplement
- Recent immigrants from regions at high risk of rickets (in the past 12 months)
- Recent refugees (in the past 12 months)
- Undernourished children
- Other chronic respiratory disease (e.g. Cystic fibrosis, Bronchopulmonary dysplasia) or chronic kidney, gastrointestinal, endocrinological or cardiac diseases, or sickle cell anemia
- History of bone disorder disease (e.g. rickets, osteomalacia)
- Intake of oral anti-epileptic, diuretic or anti-fungal medications
- Anticipated difficulty with follow-up or with adherence to the intervention or the procedures.

These criteria exclude participants prone to vitamin D deficiency, which could lead to hypocalcemia during vitamin D supplementation. They also exclude children already taking or planning to take over 400 IU/day of vitamin D, to prevent dilution of the treatment effect. Additionally, conditions or circumstances that could interfere with vitamin D metabolism or study follow-up are excluded to ensure reliable results.

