- Mean duration of use of β 2-agonist was used during each cold/asthma flare-up reported verbally or documented on the validated written 'Asthma Flare-up Diary for Young Children' over the time frame of 7 months (with each means of recording considered as a separate outcome).
- Mean of out-of-pocket asthma related expenses per exacerbation
- The sum of the daily ADYC scores as a measure of the severity of asthma symptoms during exacerbations, completed daily by parents using the validated 17-item, each scored from 1 (best) to 7 (worst), Asthma Flare-Up Diary for Young Children symptoms (ADYC) and standardized over 7 days
- Mean intensity of β 2-agonist use reported on the diary as
 - Cumulative rescue bronchodilator use: \sum daily number of puffs from the first day until last day of use until last day of use, inclusively. Units [puffs/episode]
 - Average rescue bronchodilator score = Cumulative rescue bronchodilator use \div duration of use, units [average puffs/day]
- Mean parents' functional status during exacerbations per child
 - Reported as the mean ECAP score
 - Reported as Global functional status on a 7-point likert scale from 1-not at all, to 7-extremely

Primary Efficacy Analyses

A Poisson regression model, will be estimated, using an ITT approach, including only randomization group as a predictor and adjusting only for the stratification of randomization by clinical site. This model will be used to estimate the incidence rate ratio comparing the mean number of oral corticosteroids (OCS) per child during the 7-month follow-up by study group. If overdispersion is present, a negative binomial model will be used. If there are large variations in person-time an adjustment using an offset term will be made. Two sensitivity analysis are planned; 1) the incidence rate ratio will be stratified by the month of recruitment to explore the possibility of effect modification by seasonality and 2) the incidence rate ratio will be stratified by year of the pandemic (2000-2001) to assess the possibility of effect modification by exposure to the COVID-19 pandemic period. The original analysis plan included a fixed effect for each site. However, for sites with a very small number of recruited patients, these small sites may be grouped together.

Secondary outcome analyses

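### The all-years month-of-recruitment strata partly confound season with era, so the February-August versus September-January contrast should not be read as a season effect without an era term

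*SAP*

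**What the plan says.** Under Primary Efficacy Analyses, the SAP fits a Poisson model (negative binomial if overdispersed), "including only randomization group as a predictor and adjusting only for the stratification of randomization by clinical site". Two sensitivity analyses follow. In the first, "the incidence rate ratio will be stratified by the month of recruitment to explore the possibility of effect modification by seasonality". The second stratifies separately by pandemic year, with the years printed as 2000-2001. The two are not crossed.

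The enrolment calendar is under Analysis sets/Populations/Subgroups. It begins with restricted windows: "Recruitment occurred in the fall over 3 months (Sept to Nov) for 1 year (2018), over 5 months per year (from Sept to January"). The five-month window applied to the 2019, 2020 and 2021 seasons. The later phase reads "than year-round for another 3 years (2022-2024"), and the whole recruitment period is given as seven years.

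Eligibility was relaxed during the trial, and the SAP dates this in two ways. The Inclusion criteria put the relaxed infection criterion at "≥ 2 URTIs in past 12 months, starting from the fall of 2020 (pandemic) onwards" and date the relaxed OCS criterion "starting from the fall of 2020 (pandemic) onwards (as documented by pharmacy/medical records"). The Design paragraph of the Introduction gives the OCS criterion as "≥ 1 OCS in the past 6 months (12 months since February 2022").

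**The concern.** The stated aim is to learn whether the effect of vitamin D varies with season. Season matters in this trial: the Introduction places most exacerbations in fall and winter and says that vitamin D insufficiency increases in winter.

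The strata differ in more than season. A February-August stratum can hold only children enrolled in 2022-2024 under the relaxed criteria. A September-January stratum pools children from before, during and after the main pandemic years, under both sets of criteria. The SAP itself treats these differences as possible modifiers: it plans a separate analysis by pandemic period, and it lists past OCS use (≤2 versus >2 in the past year) as a candidate subgroup, on which the changed OCS criterion acts directly. Because month and pandemic period are examined one at a time, neither analysis adjusts for the other. Larger strata would not cure this.

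**Working it through.** **1. Calendar.** Inputs are the enrolment periods above. I assume that each season's January is the one that follows it, that year-round enrolment ran to December 2024, and that January 2022, which fits both descriptions, counts once, in the 2021 season. The one stated total reproduces: 1 + 3 + 3 = 7 recruitment years.

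- Before February 2022: 3 + 3 × 5 = 18 open months, all in September-January.
- From February 2022: 35 open months. February-August has 7 × 3 = 21. September-January has 12 (September-December in three years) + 2 (January 2023 and 2024) = 14.
- Total: 18 + 35 = 53.

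| Part of year | Open months | Before Feb 2022 | Stricter criteria, change in fall 2020 | Stricter OCS criterion, change in Feb 2022 |
|---|---|---|---|---|
| Feb-Aug | 21 | 0 | 0 | 0 |
| Sept-Jan | 32 | 18 (56%) | 8 (25%) | 18 (56%) |

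The 8 months are September-November 2018 (3) and September 2019 to January 2020 (5). On either date, no February-August recruit entered under the stricter criteria. Counting January 2022 as year-round instead gives 17/32 = 53% early. Within September-January the early share is similar from month to month: 4/7 in September, October and November, 3/6 in December, 3/5 in January.

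**2. Apparent season effect when only era modifies the treatment effect.** Let p be the early-era share of September-January children. With equal control rates in both eras:

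- IRR(Sept-Jan) = p × IRR(early) + (1 − p) × IRR(late)
- IRR(Feb-Aug) = IRR(late)
- Apparent season ratio = IRR(Sept-Jan) / IRR(Feb-Aug); the truth is 1.00

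Accrual by month is not given, so p is assumed to lie between 0.3 and 0.7. The SAP's target of a 25% reduction supplies 0.75.

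- Early 0.75, late 1.00: p = 0.3 gives 0.225 + 0.700 = 0.925; p = 0.7 gives 0.525 + 0.300 = 0.825. The ratio is 0.83-0.93.
- Early 1.00, late 0.75: p = 0.3 gives 0.825/0.75 = 1.10; p = 0.7 gives 0.925/0.75 = 1.23.
- Second case with uniform accrual per open month, p = 18/32: 0.891/0.75 = 1.19. If the early control rate was half the later one, the early weight is 9/(9 + 14) = 0.39, and the ratio is 0.848/0.75 = 1.13.
- Eligibility alone as modifier, fall 2020 date, p = 0.25: 0.8125/0.75 = 1.08.

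**3. After the fix.** Among recruits from February 2022, or with a treatment-by-era term, both parts of the year have IRR(late), and the ratio returns to 1.00.

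**4. Precision.** Uniform accrual gives 323 × 32/53 = 195 September-January and 323 × 21/53 = 128 February-August children. Take the 1.19 scenario, an assumed control mean of 1 OCS per child and Poisson variance. The variance of the log ratio is then 1/64 + 1/48 + 1/97.5 + 1/(97.5 × 0.89) = 0.058, and the 95% interval factor is exp(1.96 × 0.241) = 1.6. At control means of 0.5 and 1.5 the factors are 1.95 and 1.47, so the interval around 1.19 is about 0.61-2.32 or 0.81-1.75.

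**The case against.** The strongest reply is that this is an exploratory sensitivity analysis with no decision rule. The SAP says only that it explores a possibility, and most subgroup variables correlate with something else. That stands as far as weight is concerned: nothing here touches the primary result. It does not remove the point, because the overlap with era is built into the enrolment calendar, is known in advance, and is cheap to handle.

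Second, differences in baseline rate or case-mix between eras do not by themselves distort a comparison of rate ratios. The treatment ratio must differ by era or eligibility, and nothing in the SAP shows that it does. This stands as a condition on the finding. The separate pandemic stratification would give some warning, but it is not crossed with month and does not cover the eligibility change.

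Third, the illustration is an extreme one, with the whole target effect in one era and none in the other, and even then the distortion lies well inside the sampling noise. This also stands. A wide interval does not make the estimate answer the season question, however.

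Thin monthly strata (323/12, about 27 children) are a separate matter. Pooling months into seasons would leave the confounding in place.

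**Conclusion.** The planned strata partly confound season with era and eligibility. The affected comparison is February-August against September-January, and the distortion arises only if era or eligibility modifies the treatment effect. The illustrative ratios of 0.83-0.93 and 1.10-1.23 rest on assumed accrual shares, equal control rates and a large difference in effect between eras. The calendar counts rest only on the enrolment periods and the stated reading of January 2022 and of the end of recruitment. The stricter-eligibility share is 25% or 56% according to which of the SAP's two dates applies.

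A reader might infer that this trial cannot separate season from era at all. The SAP does not support that: September-January enrolment continued in 2022-2024, so the overlap needed to separate them exists. Nor does it follow that the monthly rate ratios or the primary estimate are biased. Randomisation protects the contrast within each month, and the primary model does not depend on month.

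The change is worth making as an inexpensive improvement to a secondary question.

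**What to change.** Replace the month stratification with one sensitivity model on all 323 children that contains treatment, site, season, era, treatment-by-season and treatment-by-era. Interpret the season interaction conditional on era. Repeat it as support in children recruited in the year-round period. State that unadjusted all-years month strata, if shown, are descriptive and are not evidence of a season effect.

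Before era is defined, reconcile the Design paragraph with the Inclusion criteria on when the OCS criterion changed, and correct the pandemic years, since 2000-2001 precedes the start of recruitment in 2018. A workable cut, subject to that, is 2018 to early 2020, fall 2020 to January 2022, and February 2022 onward.

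The cost is a little SAP text, one changed model and a wider interval. Early-era children all lie in September-January, so once era is in the model the contrast with February-August is informed essentially by the year-round recruits: about 323 × 35/53 = 213 children under uniform accrual (85 and 128). With a control mean of 1 and IRR 0.75, the variance is 1/64 + 1/48 + 1/42.7 + 1/32 = 0.091, and the interval factor rises from about 1.6 to exp(1.96 × 0.302) = 1.8. The primary analysis is unchanged.

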The **ITT sample** includes all participants who are randomized into the study, regardless of whether they adhere to the study protocol or complete the study. The **per protocol sample** includes participants who adhered strictly to the study protocol without major deviations. This means they received the correct Study drug, swallowed more than 50% of Study Bolus, missed daily supplement intake for fewer than 40 days (or less than 20% of expected intake), did not experience unblinding of the study treatment and were eligible at randomization. For patients with a low daily Ca intake (< 350mg if aged 1-3 years; < 500 mg if aged 4-6 years), the bolus was administered only after receiving normal results for Ca, Ph, and ALP analyses. Additionally, there were no deviations impacting patient safety, rights, welfare, or data integrity.

The **complete case sample** includes all participants who completed the 7-month study period and provided the necessary data for primary and secondary endpoints. This includes participants who may have experienced major protocol deviations, such as incorrect study drug administration or missed daily supplements for up to 40 days, as well as minor deviations, such as delayed urine sample collections, as long as they did not withdraw from the study and their data is available for analysis.

Seven **subgroup analyses** were pre-specified at the start of the study as being of interest because of the potential for the relationship between vitamin D and asthma related outcomes to be modified by these characteristics. These include; Serum 25OHD Levels, ICS Therapy (Pre-emptive vs. Daily), Clinical Asthma Phenotype, Sex, Atopy, BMI category at baseline, Skin color according to the 6 category Fitzpatrick scale. An additional three variables were identified before analysis by group or unblinding, for exploration of subgroup effects. These include: Type 2 inflammation, OCS in the past 12 months, and step therapy using the GINA 2024 definitions.

Exposure(s), Endpoint(s) and Covariates

Exposure(s) of interest

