Secondary outcomes will be analyzed using the same modeling strategy as the primary efficacy analysis. For outcomes collected as count variables (e.g. number of laboratory-confirmed viral upper respiratory tract infections (URTIs), days with asthma symptoms, days of rescue B agonist use, number of lost parental workdays) we will again use a Poisson or negative binomial model for differences by intervention group and adjusted only for study site.

For continuous outcomes including: severity of symptoms, duration of asthma symptoms per exacerbation, duration and intensity of rescue β_2 -agonists use per exacerbation, and functional status we will compare outcomes by treatment group using a generalized linear regression model approach. For outcomes with repeated measures, a GEE method will be used adjusting for the clustering of events in individual children and if indicated an offset variable for variations in person-time if relevant.

For binary outcomes, including treatment intensification, a generalized linear model with a log-linear link function will be used, again including a GEE method to adjust for repeated measures. All confidence intervals will be constructed using robust standard errors. No adjustment for multiple outcomes is planned.

Safety Outcomes:

The Mantel-Haenszel method, stratified by clinical site, will be used to compare dichotomous outcomes including:

- The proportion of children with at least one clinically significant occurrence of hypercalciuria and hypercalcemia,
- The proportion of children with one or more occurrences of elevated serum 25OHD (>250 nmol/L)
- Proportion of children experiencing an adverse event
- Proportion of children experiencing a serious adverse event

Documented adverse and serious adverse events will be summarized according to type using MEDRA classifications.

Significance thresholds:

A two-tailed alpha of 5% will be used for all statistical tests, ensuring that the results are assessed for significance on both ends of the distribution. One interim analysis was planned once 50% of patients have been recruited and their primary endpoint assessed. The O'Brien-Fleming stopping rules were meant be applied, with p-values for the two looks (one interim and one final) set at 0.003051 and 0.046946, respectively. As nearly all the nominal alpha is preserved for the final look, no adjustment to sample size is needed.

Subgroup Analyses

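### The final-look threshold of 0.046946 is not the O'Brien-Fleming nominal p-value (0.0490), and the SAP does not say whether it or 5% decides the primary test

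*SAP*

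**What the plan says.** All the threshold statements stand in one paragraph of the SAP, under Significance thresholds. It opens with a general rule: "A two-tailed alpha of 5% will be used for all statistical tests". It then turns to the sequential plan: "One interim analysis was planned once 50% of patients have been recruited and their primary endpoint assessed". The next sentence begins "The O'Brien-Fleming stopping rules were meant be applied" and continues "with p-values for the two looks (one interim and one final) set at 0.003051 and 0.046946, respectively". The paragraph closes by arguing, in the present tense, that the sample size needs no adjustment because almost all of the alpha remains for the final analysis.

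The section on Primary Efficacy Analyses gives the model but no significance threshold.

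Two other places bear on whether the look happened. The Design paragraph of the Introduction reports "Overall, 323 (of the target of 865) children", and Analysis sets/Populations/Subgroups confirms that "The analysis sample (n=323) includes all randomized participants". The latter section also says of the late subgroup variables: "An additional three variables were identified before analysis by group or unblinding".

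**The concern.** There are two linked problems.

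1. **The final value does not fit the method.** The text calls both numbers p-values for the two looks under O'Brien-Fleming rules. In a group-sequential design the final nominal p-value is larger than the alpha left to spend, because the two test statistics are correlated. Here the two stated values add up to almost exactly 0.05, which suggests that the remaining alpha was written down as the final threshold.

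2. **The operative threshold is not stated.** The same paragraph gives 5% for all tests and 0.046946 for the final look. Which applies depends on whether an interim look was taken, and the SAP does not say.

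At stake is the decision rule for the primary outcome. A primary p-value between 0.0469 and 0.0500 would be positive under one sentence and negative under the other, and the choice could be made after seeing the result. The ambiguity also reaches the Subgroup Analyses section, where effect modification is considered only if the intervention effect is significant.

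**Working it through.** **Inputs from the SAP.** Overall two-sided alpha 0.05; one interim at 50%, taken as information fraction t = 0.5; stated p-values 0.003051 (interim) and 0.046946 (final); 323 randomised; target 865.

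**Step 1: the interim value.** O'Brien-Fleming-type (Lan-DeMets) spending, one-sided 0.025 doubled:

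4 × [1 − Φ(z₀.₉₈₇₅/√t)] = 4 × [1 − Φ(2.2414/√0.5)] = 0.0030506.

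This matches 0.003051 and identifies the boundary. The interim critical value is z = 2.9626.

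**Step 2: the final value that goes with it.** Let Z₁ and Z₂ be the interim and final statistics, with correlation √0.5. Solve for c in

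1 − P(|Z₁| < 2.9626, |Z₂| < c) = 0.05.

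The solution is c = 1.9686, a nominal two-sided p of **0.0490**. The stated 0.046946 corresponds to z = 1.9868.

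**Step 3: could another rule give the stated figures?**

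| Rule | Interim p | Final p |
|---|---|---|
| Stated in the SAP | 0.003051 | 0.046946 |
| O'Brien-Fleming-type spending, t = 0.5 | 0.0030506 | 0.0490 |
| Same spending formula with 0.05 entered as the total | 0.0056 | 0.0478 |
| Classical two-look O'Brien-Fleming | 0.0052 | 0.0480 |
| Haybittle-Peto, interim 0.001 | 0.001 | 0.0498 |
| Looks treated as independent | 0.003051 | 0.0471 |

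None gives the stated pair. Moving the information fraction does not help, since the interim value fits only t = 0.5. Simple subtraction comes closest: 0.05 − 0.003051 = 0.046949, which differs from the printed figure by 0.000003. Under the boundary in Step 2, 0.046949 is the probability of first rejecting at the final look. That is an error increment, not a p-value threshold.

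**Step 4: overall two-sided error under each use.**

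| Final threshold | Look at t = 0.5, interim 0.003051 | No look |
|---|---|---|
| 0.046946 | 0.0480 | 0.0469 |
| 0.0490 | 0.0500 | 0.0490 |
| 0.05 | 0.0510 | 0.0500 |

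**Step 5: power cost.** The SAP gives no power, so a range is shown. For power P at z = 1.9600, power at the stated threshold is Φ(1.9600 + z_P − 1.9868).

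- P = 50%: 48.9%, a loss of 1.1 points, which is about the maximum
- P = 80%: 79.2%, a loss of 0.8 points
- P = 90%: 89.5%, a loss of 0.5 points

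If a look at 50% had been taken, the fair comparator is z = 1.9686. For a design with 80% at 1.9600, the loss is then 79.8% to 79.2%.

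**Step 6: was the look triggered?** 0.5 × 865 = 432.5, so 433 children were needed with the primary endpoint assessed. Only 323 were randomised (323/865 = 37.3%). Against the only target shown, the trigger was not met.

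**The case against.** The strongest reply is that 0.046946 is history and not a rule in force. The 5% sentence is in the future tense, while the interim is described as something planned and intended. With 323 of 865 randomised, the 50% point was never reached. Read together, these point to a single final test at 5%, which is the remedy proposed for that case. Nor does an overall 5% conflict with dividing that 5% over two looks. The stated values sum to 0.049997, so the authors may have meant an alpha allocation and mislabelled it as p-values.

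Much of this is plausible. The look probably did not happen, and the timing of the added subgroups fits that reading. The derivation by subtraction is likely but not exact. The effect is also small: no bias, no inflation from the stated value, and a narrow window of p-values.

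It does not remove the point. The SAP never says that the look was not taken, and one could have been taken early or against a revised target. It calls 0.046946 a p-value set for the final look and then justifies the arrangement in the present tense. If the figure is an alpha allocation, it is still wrong as a threshold for the final p-value. Falling back on 5% is safe only if there was no look, because after a look at 50% it gives 0.0510. This SAP version dates from May 2025, after the 2018–2024 recruitment it describes, so the fact was available to be stated.

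**Conclusion.** The concern holds. The final-look value is wrong as written: the nominal p-value consistent with the SAP's own interim figure is 0.0490. The threshold for the primary test is also left open between 5% and 0.046946.

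The practical size is modest. The stated value is conservative, does not bias the estimate and costs at most 1.1 points of power. It alters the conclusion only if the primary p-value falls between 0.0469 and 0.0500. That is still a choice on the primary outcome that should not remain open once results are known.

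The 0.0490 figure assumes a look at exactly half information and an overall two-sided alpha of 0.05. That no look took place is an inference from the recruitment figures, not something the SAP establishes.

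**What to change.** Before unblinding, amend Significance thresholds to state whether any unblinded interim look took place and to give one threshold for the primary outcome. Repeat that threshold under Primary Efficacy Analyses.

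- **If no look took place:** test the primary outcome at two-sided 0.05. Keep 0.003051 and 0.046946 only as a record of the original design, marked as not operative.
- **If a look took place:** state its information fraction and recompute the final boundary from the joint distribution of the two statistics. At 50% it is 0.0490. By way of illustration only, it would be 0.0494 at 45% and 0.0476 at 60%.

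The cost is two sentences in the SAP, with no new data and no further analysis.
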